Stratification Groups	Study Groups	Priming Vaccination 1 (Day 0)	Priming Vaccination 2 (Day 28)	Booster Vaccination (Day 208)		
		Randomized 1:1:1:1		Booster randomization ratio: ARCT-021 : ARCT-154 : ARCT-165 : Placebo 1:1:1:1		
Younger adults ^a AND Older adults ^b	1	ARCT-021 7.5 µg	Placebo	ARCT-021 5.0 µg ARCT-154 5.0 µg ARCT-165 5.0 µg Placebo		
		ARCT-021 5.0 µg	ARCT-021 5.0 µg			
		ARCT-021 7.5 µg	ARCT-021 7.5 µg			
	4	Placebo	Placebo	If not re-enrolled at Day 98-198^c: Booster Vaccination (Day 208) Booster randomization ratio: ARCT-021 : ARCT-154 : ARCT-165 1:1:1 (No Placebo)		
				ARCT-021 5.0 µg ARCT-154 5.0 µg ARCT-165 5.0 µg		
				If re-enrolled (Day 98-198) Vaccination 1 (Day 0) Groups 1, 2, and 3 (No Placebo) Randomized 1:1:1	Vaccination 2 (Day 28)	Booster Vaccination (Day 208) 1:1:1:1 (Includes placebo)
				ARCT-021 7.5 µg	Placebo	Placebo ARCT-021 5.0 µg ARCT-154 5.0 µg ARCT-165 5.0 µg
				ARCT-021 5.0 µg	ARCT-021 5.0 µg	
				ARCT-021 7.5 µg	ARCT-021 7.5 µg	

a Younger adults: 18 to <56 years of age in US and 21 to <56 years of age in Singapore

b Older adults: ≥ 56 years of age

c See [Section 3.1](#)

4. General Statistical Considerations

Data from participants excluded from an analysis will be included in the applicable data listings but not included in the calculation of summary statistics for that analysis set.

For categorical variables, frequencies, percentages, and 95% CIs (where applicable) will be presented. All percentages will be rounded to one decimal place. The number and percentage will be presented in the form XX (XX.X), where the percentage is displayed in parentheses.

Continuous variables will be summarized using descriptive statistics (i.e., number of participants, mean, median, SD, minimum, maximum, and 95% CIs [where applicable]). All mean and median values will be formatted to one more decimal place than the actual value. Standard deviation values will be formatted to two more decimal places than the actual value. Minimum and maximum will be formatted to the same decimal place as the actual value.

When count data are presented, the percentage will be suppressed when the count is zero in order to draw attention to the non-zero counts. The denominator for all percentages will be the number of participants in the given treatment group within the analysis set of interest and stratification level (if applicable) unless otherwise specified in a footnote.

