8.2. Analysis of Immunogenicity Primary and Secondary Endpoints

8.2.1. Analysis of primary and secondary immunogenicity endpoints

Total NAbS and BAbS titers will be summarized using descriptive statistics (number of subjects (n), median, minimum and maximum) by each time point in priming vaccination period (Baseline, Days 14, 28, 42, 56, 208) and booster vaccination period (Day 208, 236, Early Termination). Summaries of priming vaccination and booster vaccination periods based on their corresponding mITT and PP analysis sets will be presented separately using the applicable treatment groups (Table 4-1). For the analysis of booster mITT analysis set, summary tables with active boosters pooled (as presented in Table 4-1; e.g., A1, A2, B1, B2, etc.) will also be presented.

The following statistics will be provided in the summary tables and/or figures:

- Geometric mean titer (GMT) with corresponding 95% CI will be provided at each time point. The 95% CIs will be calculated based on the t-distribution of the log-transformed values then back transformed to the original scale for presentation. GMT level and corresponding 95% CI will be plotted at each timepoint in priming vaccination period for mITT analysis set. Plots of the reverse cumulative distribution curves also will be provided by treatment group and visit in priming vaccination period for mITT analysis set.
- Geometric mean fold rise (GMFR) with corresponding 95% CI will be provided at each post-baseline timepoint over baseline. The 95% CIs will be calculated based on the t-distribution of the log-transformed values then back transformed to the original scale for

presentation. GMFR and corresponding 95% CI will be plotted at each timepoint in priming vaccination period for mITT analysis set.

- The number and percentage of subjects with fold-rise ≥ 2 and fold-rise ≥ 4 from baseline (Seroconversion) at each post baseline time points will be tabulated with the 2-sided 95% CI using the Clopper Pearson method at each post-baseline timepoint.
- Seropositivity at a participant level is defined as any detectable antibody level above the lower limit of quantification (LLOQ) for the specific assay and antibody measured at timepoints after baseline. Seropositivity rates will be provided with 2-sided 95% CI using the Clopper-Pearson method at each post-baseline time point.

The definition of seroconversion/seropositivity may depend on assay-specific performance characteristics. The conventions are as follows:

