8.3. Exploratory Immunogenicity Analyses

8.3.1. Assays for Response to SARS-CoV-2 Variants

To address the exploratory immunogenicity objective to evaluate responses to SARS-CoV-2 variants, the binding antibody responses of ARCT-021/ARCT-154/ARCT-165 will be compared to placebo for the booster vaccination period. SARS-CoV-2 binding antibodies (BAbs) will be tested using an MSD multiplex assay which measures total immunoglobulin G (IgG) against the full-length spike, RBD and N antigens of the beta strain. Neutralizing antibodies against the beta strain of SARS-CoV-2 will also be measured:

- IgG measured against the Nucleocapsid (N) antigen of the beta variant (B1.351) of SARS-CoV-2 (VAC83_ECL_CoV-2_N)
- IgG measured against the RBD antigen of the beta variant (B1.351) of SARS-CoV-2 (VAC83_ECL_CoV-2_RBD)

- IgG measured against the Spike antigen of the beta variant (B.1.351) of SARS-CoV-2 (VAC83_ECL-CoV-2_S_B.1.351)
- Microneutralization antibody concentration against the beta variant (B.1.351) of SARS-CoV-2 (VAC85_MN_CoV-2)

Similar estimands will be used as for the secondary objective.

The LLOQ for each assay is shown below:

- VAC83_ECL_CoV-2_N (AU/mL; 1:500 dilution): 27
- VAC83_ECL_CoV-2_RBD (AU/mL; 1:500 dilution): 19
- VAC83_ECL_CoV-2_S_B.1.351 (AU/mL; 1:500 dilution): 18
- VAC85_MN_CoV-2 (AU/mL; 1:5 dilution): 14

Assays for other variants may be analyzed as available as part of the exploratory analysis.

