8.3.3. ACE2 Receptor Exploratory Analysis

Exploratory analysis of the following sVNT ACE2 receptor binding inhibition for three strains will be performed: VAC114_ECL_CoV-2_S, VAC114_ECL_CoV-2_S_B1.351, VAC114_ECL_CoV-2_S_B1.617.2. The analysis will be similar to the analysis specified for the primary and secondary immunogenicity endpoints (section 8.2.1) and will be performed for Priming (mITT analysis set) and Booster vaccination period (Booster mITT analysis set).

The LLOQ for each assay is shown below:

VAC114_ECL_CoV-2_S, VAC114_ECL_CoV-2_S_B1.351, and VAC114_ECL_CoV-2_S_B1.617.2: 0.78125 units/mL at the 1:10 dilution and 7.8125 units/mL at the 1:100 dilution

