8.3.4. NAbs/BAbs Ratio Analysis

NAbs/BAbs ratio at each visit during priming vaccination period and booster vaccination period will be summarized using descriptive statistics by treatment group for the mITT and Booster mITT analysis sets, respectively. Binding antibody test results for both the spike protein and RBD will be included in this analysis. Neutralizing and binding antibody tests for two strains may be performed, but only NAbs/BAbs ratios derived from tests of the same strain of SARS-CoV-2 will be presented:

NAbs/BAbs Ratio	Parameter Codes	Analysis Period
Wuhan Neutralizing/Spike Binding	VAC62MN/VAC72S	Priming and Booster
Wuhan Neutralizing/RBD Binding	VAC62MN/VAC72R	Priming and Booster

Beta Neutralizing/Beta Spike Binding	VAC85MN/V83B1351	Booster Only
Beta Neutralizing/Beta RBD Binding	VAC85MN/VAC83RBD	Booster Only

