2. Protocol Section 7.6.4.2 states the following: *“Seropositivity at a participant level: is defined as a change of NAb titer from below the LOD or Lower Limits of Quantification (LLOQ) to equal to or above LOD or LLOQ (respectively), or a 4-times or higher log-transformed titer ratio in participants with pre-existing NAb titers.”* This definition has been revised in SAP Section 8.2.1 to the following: *“Seropositivity at a participant level is defined as any detectable antibody level above the lower limit of quantification (LLOQ) for the specific assay and antibody measured at timepoints after baseline.”*
 - Justification: Clarify the clinical definition of seropositivity.
3. Protocol Section 7.6.4.2 states the following: *“The common difference of seroconversion rate and 95% CI between each vaccine dose group and the placebo will be estimated using CMH method with stratification factors for each time point from Day 14 to Day 208 for the mITT.”* The Miettinen-Nurminen method will be used instead of the CMH method as stated in SAP Section 8.2.2.2.
 - Justification: CMH uses normal approximation, Miettinen-Nurminen has better coverage property than CMH.

4. Protocol Table 2.3 states that BAbs/NAbs ratio will be summarized. This was revised to have the neutralizing antibodies as the numerator and the binding antibodies as the denominator instead because neutralizing antibodies are a subset of binding antibodies.

12. References

Arcturus Therapeutics, Inc., protocol ARCT-021-04 (A PHASE 2 RANDOMIZED, OBSERVER-BLIND, PLACEBO-CONTROLLED STUDY TO ASSESS THE SAFETY, REACTOGENICITY, AND IMMUNOGENICITY OF THE SARS-CoV-2 VACCINE ARCT-021 IN HEALTHY ADULT PARTICIPANTS) Version 6.0, dated 09 March 2022.

SAS Institute Inc. 2008. SAS/STAT® 9.2 User's Guide. Cary, NC: SAS Institute Inc.

13. Appendices

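### The NAb/BAb ratio in SAP 8.3.4 falls to a default of raw-scale mean and SD, although every other antibody measure in the SAP is summarised on the log scale (minor)

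*SAP*

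**What the plan says.** SAP 8.3.4 covers four ratios: Wuhan neutralising over spike and over RBD binding in both periods, and the two beta-variant counterparts in the booster period only. The whole instruction on how to summarise them is that the ratio at each visit in the priming period and "booster vaccination period will be summarized using descriptive statistics by treatment group for the mITT and Booster mITT analysis sets". The ratio row of the table in SAP 8.4 names a summary table and no statistic, whereas the NAb, BAb and sVNT rows list GMT and GMFR.

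SAP section 4 gives the general rule: "Continuous variables will be summarized using descriptive statistics (i.e., number of participants, mean, median, SD, minimum, maximum", with 95% CIs where applicable.

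Other antibody measures have their own rule:
- **Wuhan NAb and BAb (SAP 8.2.1):** "Total NAbS and BAbS titers will be summarized using descriptive statistics (number of subjects (n), median, minimum and maximum) by each time point". GMT and GMFR are added, and "The 95% CIs will be calculated based on the t-distribution of the log-transformed values then back transformed to the original scale for presentation".
- **Beta-variant NAb and BAb (SAP 8.3.1):** "Similar estimands will be used as for the secondary objective".
- **ACE2 binding inhibition (SAP 8.3.3):** "The analysis will be similar to the analysis specified for the primary and secondary immunogenicity endpoints (section 8.2.1").

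The direction of the ratio also changed. Protocol Table 2-3 lists BAbs/NAbs among the exploratory booster endpoints. SAP section 11, item 4, reports: "This was revised to have the neutralizing antibodies as the numerator and the binding antibodies as the denominator instead".

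**The concern.** Section 8.3.3 points back to 8.2.1 and section 8.3.4 does not, so a programmer would apply the section 4 default to the ratio and produce an arithmetic mean and SD of the raw values. Yet the ratio is formed from the same assays that the SAP log-transforms everywhere else.

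On the raw scale the mean has two unwelcome properties. It increases with the between-person variability of the ratio even when the typical ratio is unchanged. It also has no simple relation to the mean of the inverse ratio, so the choice of numerator, which differs between protocol and SAP, affects more than presentation. On the log scale exchanging numerator and denominator only changes the sign.

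What is at stake is how one exploratory table reads when treatment groups are set side by side, chiefly the booster groups.

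**Working it through.** **Inputs**
- SD of one antibody titre on the natural-log scale: 1.2, with a CoV of 180% (SAP 4.2, Protocol 7.3). This is the only SD in the documents.
- Assumption: the same SD of 1.2 applies to both the neutralising and the binding assay.
- Assumption: the correlation r between log NAb and log BAb is 0.5 to 0.9. The documents give no value.

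**The plan's own figure.** For a log-normal variable, CoV = sqrt(exp(SD²) − 1) = sqrt(exp(1.44) − 1) = 1.795, or 179.5%. This agrees with the stated 180%.

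**Formulas for the ratio**
- SD of ln(NAb/BAb): s = 1.2 × sqrt(2(1 − r))
- Arithmetic mean / geometric mean = exp(s²/2)
- Mean(NAb/BAb) × mean(BAb/NAb) = exp(s²). A summary that merely inverted with the ratio would give 1.

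| r (assumed) | s | Arithmetic / geometric mean | Product of the two arithmetic means |
|---|---|---|---|
| 0.5 | 1.20 | exp(0.720) = 2.05 | exp(1.440) = 4.22 |
| 0.7 | 0.93 | exp(0.432) = 1.54 | exp(0.864) = 2.37 |
| 0.9 | 0.54 | exp(0.144) = 1.15 | exp(0.288) = 1.33 |

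A simulation of about one million ratios at s = 1.2 and geometric mean 1 gave a mean of 2.05 for the ratio, 2.05 for its inverse, and a median of 1.00.

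**What does not depend on the assumptions.** For any positive variable that is not constant, the arithmetic mean exceeds the geometric mean, and the product of the mean and the mean of the inverse exceeds 1. The assumed r sets only the size.

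**On the log scale.** The geometric mean carries no spread term, and geometric mean(NAb/BAb) × geometric mean(BAb/NAb) = 1 exactly.

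**The median.** For a log-normal ratio the population median equals the geometric mean, so it does not move with spread and it inverts with the ratio.

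**The case against.** The best counter-argument is that 8.3.4 never mentions an arithmetic mean, an SD or the raw scale. Section 8.2.1 uses the same term for a shorter list (n, median, minimum, maximum), and 8.3.2 spells out mean and SD where they are wanted. A reader could therefore borrow the 8.2.1 list. This stands in part: the mean and SD are inferred from section 4. But the 8.2.1 list is written for titres and 8.3.4 does not refer to it. Even on that reading the ratio would have neither a geometric mean nor an interval.

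Second, the median appears under either reading and has neither defect. This stands, and it limits the point to the mean, the SD and any interval around the mean. A geometric mean ratio can also be recovered by dividing the GMTs if the same participants contribute to both, though its interval cannot, because that needs the within-person pairing.

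Third, the direction is pre-specified with a reason, so no choice is left open after the data are seen. This stands too.

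Stronger readings are tempting, and the documents do not support them:
- **That intervals for the ratio will cover poorly at 25 per group.** Neither 8.3.4 nor its row in 8.4 plans an interval. The figure of 25 matches 75/3, one age cohort of Study Group 4, but the ratio row has no age breakdown and SAP Table 4-1 pools the ARCT-primed regimens. Planned booster groups are about 112 ARCT-primed (600 × 3/4 = 450; 450/4) and 50 placebo-primed (600/4 = 150; 150/3), before attrition and re-enrolment.
- **That spread alone will separate the groups by some particular factor, or that the flip will reorder them.** Both are possible. For example, geometric means of 1.0 and 1.3 with log-SDs of 1.2 and 0.6 give mean NAb/BAb of 2.05 and 1.56, but mean BAb/NAb of 2.05 and 0.92. Those values are invented, and nothing in the documents suggests that the groups differ in spread.

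**Conclusion.** The point holds as a minor one. As written, SAP 8.3.4 leads by way of the section 4 default to a raw-scale arithmetic mean and SD, out of line with every other antibody measure in the SAP. CMI in 8.3.2 also uses mean and SD, but it is not an antibody measure. The mean would exceed the typical ratio 2.05-fold to 1.15-fold, given a log-SD of 1.2 for both assays and a correlation of 0.5 to 0.9. The direction of the effect is certain; its size rests on those two assumptions.

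A reader might infer that the booster comparison is unreliable. The documents do not support that. The ratio is one item under an exploratory objective, with no model or decision rule. Protocol 7.2 and 7.6.1 exclude hypothesis testing and call the analysis descriptive, and the SAP introduction already warns that interpretation may be limited after Day 56. The median remains a sound summary, though without a planned interval. No primary or secondary result is affected.

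**What to change.** In SAP 8.3.4 and the ratio row of 8.4, name the statistics: the geometric mean of NAb/BAb by treatment group and visit, with a two-sided 95% CI from the t-distribution of ln(NAb/BAb), back-transformed as in 8.2.1, together with n, median, minimum and maximum. State that the arithmetic mean is not used as the group summary.

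The cost is a few words in the SAP and re-use of the GMT program on the within-participant ratio. It needs no new data and changes no other table.

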8.4. Summary of Immunogenicity Endpoints Analyses

Parameter	Statistics ¹	Analysis set	Vacc. Period ²	Age group <56 and ≥ 56	Age group <65 and ≥ 65	Gender	Country
Primary: SARS-CoV-2 Neutralizing Antibody (Estimands 2 and 3)	Table: Summary GMT/GMFR/SC/SP	mITT	P	x	x	x	x
		PP	P	x			
		Booster mITT	B	x	x		
		Booster PP	B	x			
	Figure: GMT Over Time	mITT	P	x		x	x
	Figure: GMFR Over Time	mITT	P	x		x	x
	Figure: RCDF at each time point	mITT	P	x		x	x
	Table: ANCOVA Model	mITT	P	x		x	x
	Table: Miettinen-Nurminen for SC/SP Rates	mITT	P				
Secondary: SARS-CoV-2 Binding Antibody (Estimands 2 and 3)	Table: Summary GMT/GMFR/SC/SP	mITT	P	x	x	x	x
		PP	P	x			
		Booster mITT	B	x	x		
		Booster PP	B	x			
	Figure: GMT Over Time	mITT	P	x		x	x
	Figure: GMFR Over Time	mITT	P	x		x	x
	Figure: RCDF at each time point	mITT	P	x		x	x
	Figure: scatterplot binding/neutralizing antibody	mITT	P	x		x	x
	Table: ANCOVA Model	mITT	P	x		x	x
	Table: Miettinen-Nurminen for SC/SP Rates	mITT	P				
Exploratory: CMI	CMI responses	mITT-CMI	P	x			
		PP-CMI	P	x			
		Booster mITT-CMI	B	x			

	Box plots: CD4+/CD8+ IFN γ , IL4+IL13+, IFN γ +/IL4+IL13+, Th1/Th2	mITT-CMI	P	x			
Exploratory sVNT (ACE2 receptor binding inhibition)	Table: Summary GMT/GMFR/SC/SP	mITT	P				
		Booster mITT	B				
NAb/BAb ratio	Table: Summary NAb/BAb Ratio	mITT	P				
		Booster mITT	B				

¹BAbs = Binding Antibodies, NAb = Neutralizing Antibodies, GMT=Geometric mean titers, GMFR=Geometric Mean Fold-rise, SC=Seroconversion, SP=Seropositivity, RCDF=Reverse Cumulative Distribution Function.

²P=Priming Vaccination Period: All timepoints up through Day 208 (prior to booster vaccination). B=Booster Vaccination Period: All timepoints from Day 208 through Early Termination.

9. Safety Analysis

All safety summaries and analyses will be conducted for the Safety analysis sets. All safety data collected will be summarized by defined duration relative to each vaccination, as well as for overall study by treatment group.

Safety and reactogenicity will be assessed by clinical review of all relevant parameters including solicited local and systemic AE, unsolicited AEs, new onset of chronic disease (NOCD), medically attended adverse events (MAAEs), AEs leading to next vaccine delayed or vaccine will not be re-dosed and SAE through early termination. Any AE that leads to discontinuation of the vaccine and/or withdrawal from the study will be regarded as an AE leading to discontinuation/withdrawal.

9.1. Adverse Events

Adverse Event (AE) collection will begin after the signing of informed consent; however, AEs that occur prior to the administration of first dose of study vaccine (i.e., non-treatment-emergent AEs) will be listed in the clinical study report. MedDRA version 23.0 or higher will be used for coding to System Organ Class (SOC) and Preferred Term.

Any case of confirmed COVID-19 or asymptomatic SARS-CoV-2 infection will be regarded as a Clinical Event of Special Interest (CESI) and entered on the CRF as an Adverse Event. Because CESI events are typically associated with the disease under study, they will not be reported as suspected unexpected serious adverse reaction (SUSAR) but on the CESI eCRF page.

Summaries of number of participants (%) with solicited AEs (by toxicity grade), safety laboratory assessments (by toxicity grade), unsolicited AEs (by severity and relatedness to study vaccine), MAAEs, NOCDs, and AEs leading to discontinuation/withdrawal will be presented and

also with a focus on those related to vaccine administration. All summaries will be evaluated by study treatment group as well as vaccine administration (first dose, second dose, booster dose).

Incomplete AE onset and end dates will be imputed according to the rules specified in [Appendix 2](#).

9.1.1. Reactogenicity

Any solicited local or systemic AE initiation within 7 days after each priming vaccination will be summarized by vaccination and by toxicity grade as number and percentage of participants. A summary by grade group (Grade 0 through 4 and Grade 1 through 4) will also be presented with 2-sided 95% CI using the Clopper-Pearson method. Grade 0 is a reported symptom lower than Grade 1. The duration of solicited local and systemic AEs after each vaccination will also be summarized. For injection site erythema, injection site induration/swelling, and diarrhea the duration for events graded 0 to 4 will be summarized. For all other solicited events, the duration for events graded 1 to 4 will be summarized.

Solicited local and systemic AEs through 7 days following each study vaccination will be evaluated by the participant and recorded in the diary as the following:

- Solicited local AEs: injection site erythema, injection site pain, injection site induration/swelling, injection site tenderness
- Solicited systemic AEs: arthralgia, chills, diarrhea, dizziness, fatigue, fever (categorized by measured body temperature), headache, myalgia, nausea/vomiting

Data will also be summarized by age group (≥ 18 to <56 years; ≥ 56 years).

The toxicity grade will be categorized by application of the DHHS CBER Toxicity Grading Scale. Participants will be counted once for the most severe event in cases where the participant reported more than one event per solicited AE category (e.g., pain).

For re-enrolled subjects and the booster vaccination period, summary of solicited AEs within 7 days post each vaccination by toxicity grade and age group will also be performed. In addition, a summary of solicited adverse events within 7 days post booster vaccination by grade and age group with active boosters pooled (as presented in Table 4-1; e.g., A1, A2, B1, B2, etc.) will be presented.

In addition, summary of solicited adverse events within 7 days post each priming vaccination by grade group and age group (≥ 18 to <65 years; ≥ 65 years) for Reactogenicity analysis set will be provided.

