The first-in-human study ARCT-021-01 has completed with 106 participants enrolled and vaccinated with either ARCT-021 (N=78) or placebo (N=28). The study was conducted in healthy adult participants in Singapore. At the time of IB version 4.0 finalization, the study report is not final but the available data are summarized in the IB.

Analysis of the open-label extension study ARCT-021-02 has not yet been conducted.

At the time of IB version 4.0 finalization, the present study has completed enrollment of 579 participants. Two interim analyses have been conducted. Across the analyzed clinical experience to date, ARCT-021 has been generally safe and well tolerated at doses ≤ 7.5 μ g. In study ARCT-021-01, the 10- μ g dose tested was associated with more systemic AEs,

Arcturus Therapeutics, Inc.
Protocol ARCT-021-04, Version 6.0

ARCT-021
09 March 2022

including Grade 3 events. In the clinical trials conducted thus far, no vaccine-related SAEs have occurred in ARCT-021-treated participants, and 8 AEs have led to discontinuation.

Most (>90%) ARCT-021-treated participants in each study experienced at least one solicited AE. In each study, the majority of solicited events were Grade 1/mild or Grade 2/moderate. A single participant reported Grade 4 solicited events (dizziness, fatigue, nausea, chills, headache).

The most common solicited AEs were injection site pain, injection site tenderness, headache, fatigue, myalgia, arthralgia and chills. The majority of solicited events had onset on the day after dosing and were no longer reported by the end of 7 days post-dose.

In the ARCT-021-01 study, the overall incidence of solicited events was generally lower in older adults but in the phase 2 study, which represents the largest exposure at clinically relevant doses (ie, 5 µg and 7.5 µg), the incidence was similar between younger and older adults.

Solicited AE reporting appears to decline slightly with second dose of ARCT-021. There may be a slight increase in Grade 3 solicited AE reporting following dosing with 7.5 µg ARCT-021 as compared with 5 µg ARCT-021.

Unsolicited AE reporting is less frequent following ARCT-021 as compared to solicited AEs. The most common unsolicited AEs in both studies include headache, fatigue, injection site tenderness, diarrhea, elevated CPK, neutropenia, lymphopenia, urticaria and hematuria, which was not confirmed on microscopy.

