4.2.2 Discontinuation of Study Vaccine (Participant)

Additional administrations of study vaccine are absolutely contraindicated for any of the following reasons:

- Grade 3 solicited AEs (as confirmed by Investigator review), severe anaphylaxis, severe related (possibly, probably, or definitely) unsolicited AEs, or immediate type hypersensitivity (≤ 4 hours after injection) following the administration of the study vaccine.
- Any SAE judged to be related (possibly, probably, or definitely) to vaccine.
- Pregnancy in a female participant.
- Any clinically significant medical condition that, in the opinion of the Investigator, poses an additional risk to the participant if he/she continues to participate in the study.
- New information becomes available that makes further participation unsafe.

Arcturus Therapeutics, Inc.
Protocol ARCT-021-04, Version 6.0

ARCT-021
09 March 2022

A participant should not receive subsequent administrations of study vaccine for any of the following additional reasons:

- Participant receives an off-study COVID-19 vaccine
- Participant is lost to follow-up.
- As deemed necessary by the Investigator for non-compliance or other reasons. This may include previously undisclosed or new conditions that meet exclusion criteria.
- Termination of the trial.

If any of these events occur during the study, then the participant must not receive additional doses of study vaccine. Furthermore, the participant will be encouraged to continue study participation for safety and immunogenicity evaluations through the Early Termination Visit after the first vaccination.

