4.4.7. Reactogenicity Analysis Set

The Reactogenicity analysis set (RAS) includes all participants who receive any dose of priming study vaccine (ARCT-021 or placebo) and provide at least 1 reactogenicity diary report for the time period evaluated. Participants will be analyzed according to the vaccine received.

- Note: The RAS for re-enrolled participants consists of all re-enrolled participants who receive any dose of study vaccine while as a re-enrolled participant and provide at least 1 reactogenicity diary report for the time period evaluated.

The following analysis sets will be applicable for the Booster Vaccination Period:

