4.6. Missing Data Handling and Imputation Rules

No missing safety and reactogenicity results will be imputed. Incomplete AE onset and end dates will be imputed according to the rules specified in [Appendix 2](#). For safety analysis, percentages will be based on the analysis set of interest (e.g., Safety Set) within each treatment group and overall for the relevant vaccination/period of interest. For reactogenicity analysis, the denominator will be number of participants in the reactogenicity analysis set for the relevant vaccination/period of interest.

Any immunogenicity results that are below the limit of detection (LOD) or lower limit of quantification (LLOQ) will be imputed as half of the corresponding limit and results above the upper limit of quantification will be imputed as that limit for analysis purposes.

5. Participant Disposition and Protocol Deviations

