5.1. Participant Disposition

The number and percentage of participants in the following categories (analysis sets defined in [Section 4.4](#)) will be summarized based on the following (where applicable):

- Randomized Set
- Intent-to-Treat Set
- Modified Intent-to-Treat Set (mITT)
- Per-Protocol Set (PP)
- Cell Mediated Immunity Analysis Subsets (CMI)
 - mITT-CMI
 - PP-CMI
- Safety Set

- Reactogenicity Set (Dose 1)
- Reactogenicity Set (Dose 2)
- Booster Randomized Set
- Booster Safety Set
- Booster Reactogenicity Set
- Booster Intent-to-Treat Set (Booster ITT)
- Booster Modified Intent-to-Treat Set (Booster mITT)
- Booster Per-Protocol Set (PP)
- Booster Cell Mediated Immunity Subset (Booster CMI)
 - Booster mITT-CMI
 - Booster PP-CMI

The number of participants in the following categories will be summarized based on participants screened:

- Number of participants screened
- Number and percentage of screen failure participants and the reason for screen failure

The number and percentage of participants in each of the following disposition categories will be summarized based on the Randomized set for the priming vaccination period:

- Received each dose of study vaccine for priming vaccination dose 1 and dose 2
- Prematurely discontinued before receiving the second dose of study vaccine and the reason for discontinuation
- Prematurely discontinued before receiving the booster dose of study vaccine and the reason for discontinuation
- Completed study
- Prematurely discontinued the study and the reason for discontinuation

A participant disposition listing will be provided, including informed consent, participants who completed the study injection schedule, participants who completed study, participants who discontinued from study vaccine or who discontinued from participation in the study, with reasons for discontinuation. Randomization data will be also provided in a listing.

A table summarizing the frequencies and percentages for the following will be provided by the primary vaccination treatment groups for Safety Analysis set:

- Participants who have completed booster vaccination and who are followed for 56 days post booster vaccination or less
- Participants who have completed booster vaccination and who have been followed longer (> 56 days but < 180 days after booster dose)
- Participants who have completed primary vaccination and who have been followed < 12 months

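### SAP 9.1.1 specifies solicited-AE tables only dose by dose, so the Dose 2 Grade 3+ rate is conditional on no confirmed Grade 3 reaction at Dose 1, and no table gives reactogenicity over the whole priming course

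*SAP*

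**What the plan says.** SAP 9.1.1 sets the tabulation rule for solicited events: "Any solicited local or systemic AE initiation within 7 days after each priming vaccination will be summarized by vaccination and by toxicity grade". SAP 4.6 adds that "the denominator will be number of participants in the reactogenicity analysis set for the relevant vaccination/period of interest". Under SAP 4.4.7, entry to that set requires a participant to be dosed and to "provide at least 1 reactogenicity diary report for the time period evaluated". The disposition list in SAP 5.1 names a Dose 1 set and a Dose 2 set for the priming period, with no either-dose set.

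Protocol 4.2.2 states: "Additional administrations of study vaccine are absolutely contraindicated for any of the following reasons". The first item listed begins "Grade 3 solicited AEs (as confirmed by Investigator review), severe anaphylaxis".

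On experience so far, Protocol 1.5 says: "Solicited AE reporting appears to decline slightly with second dose of ARCT-021". The same section suggests that Grade 3 solicited events may be slightly more frequent after 7.5 µg than after 5 µg, but gives no rate.

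Selecting the dose and schedule is a primary objective (SAP Table 2-1). The safety estimand handles a missed dose by treatment policy (SAP Table 13-4).

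**The concern.** The event that stops a participant from receiving Dose 2 is itself one of the outcomes tabulated. This is no criticism of the stopping rule. The point is what the rule does to a table built only from people who went on to Dose 2. If people who react strongly once tend to do so again, the Dose 2 group is less reactive than the group that started, and the Grade 3+ rate can appear to fall when nothing has changed. A group with more Grade 3 reactions at Dose 1 also loses more of its reactive members, which narrows Dose 2 differences between groups.

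The second gap concerns the regimen. The study sets one active dose (Group 1) against two (Groups 2 and 3). A natural question is what share of participants had a Grade 3+ reaction at any time in the priming course. Two per-dose rates on different denominators do not answer it. A Dose 2-recipient denominator also sits poorly with a treatment-policy strategy for missed doses.

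**Working it through.** **Is an any-dose solicited-AE table specified anywhere?**
- SAP 9.1.1: per vaccination only, by grade, grade group and age group.
- SAP 9.1.2.2: has an overall pre-booster period, but for unsolicited AEs.
- SAP 7.1: has a summary within 7 days of either priming dose, but for concomitant medications.
- SAP section 9 (opening text) and Protocol 7.6.3.2: promise overall summaries of safety in general terms. Neither is carried into a solicited-AE table.

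**The plan's own figure.** The safety sample size rests on p = 1 − (1 − R)^N. With R = 1% and N = 75, 1 − 0.99^75 = 0.529, as stated. If 5% of 75 were barred from Dose 2 (about 4 people, leaving 71), 1 − 0.99^71 = 0.510. The loss of numbers hardly matters; the question is who is lost.

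**Illustration of the selection.** The documents give neither a Grade 3 rate nor a within-person correlation, so both are assumed. Let p be the true Grade 3+ rate, the same at both doses. Severity at the two doses is bivariate normal with correlation ρ, and Dose 2 is withheld after Grade 3+ at Dose 1. Let j be the probability of Grade 3+ at both doses if everyone were dosed twice.

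- Rate shown in the Dose 2 table = (p − j) / (1 − p)
- Any-dose rate over all dosed = p + (p − j)

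Worked case, p = 5% and ρ = 0.5: j = 0.0122. The Dose 2 rate is (0.05 − 0.0122) / 0.95 = 4.0%. The any-dose rate is 0.05 + 0.0378 = 8.8%.

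| True rate at each dose | ρ | Dose 2 table shows | Any-dose rate |
|---|---|---|---|
| 5% | 0 | 5.0% | 9.8% |
| 5% | 0.3 | 4.5% | 9.3% |
| 5% | 0.5 | 4.0% | 8.8% |
| 5% | 0.7 | 3.2% | 8.0% |
| 10% | 0 | 10.0% | 19.0% |
| 10% | 0.3 | 8.7% | 17.8% |
| 10% | 0.5 | 7.5% | 16.8% |
| 10% | 0.7 | 5.9% | 15.3% |

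At ρ = 0, j = p² and the Dose 2 rate equals p, so there is no distortion.

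**Between groups.** Take one group at 5% and another at 10%, at each dose. The true Dose 2 difference is 5.0 points. The tables would show 4.2, 3.5 and 2.7 points for ρ = 0.3, 0.5 and 0.7. The any-dose difference would be 8.6, 8.0 and 7.3 points.

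**Any-grade rates.** With an assumed 90% any-grade rate at each dose and the same model, the Dose 2 figure falls by 0.4 to 0.5 points when the Grade 3+ rate is 5%, and by 0.8 to 1.1 points when it is 10%.

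**A both-doses-only comparison is not a remedy.** Anyone with a confirmed Grade 3 event at Dose 1 should have no Dose 2. Restricting to people with both doses therefore sets the Dose 1 confirmed Grade 3 rate to zero by construction. In the worked case it would show a spurious rise from 0% to 4.0%.

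**The case against.** The participants who drop out of the Dose 2 table are not lost to the report. Protocol 6.4.1.1.1 captures a solicited AE that leads to discontinuation as an unsolicited AE as well. SAP 9.1.2.1 and 9.1.2.2 summarize such events on the Safety set, including the overall pre-booster period. SAP 5.1 counts those stopped before Dose 2, with the reason. This stands, and a separate footnote count would add little. But these tables give neither the maximum solicited grade over the course nor a correction to the Dose 2 rate.

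Per-vaccination reporting is also the declared endpoint, and the study is descriptive with no hypothesis tests. That stands too: no error rate is at issue, and the per-dose tables should stay. The gap is that the overall summary promised elsewhere has no specified form for solicited AEs.

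Three stronger readings are tempting, and the documents do not support them.
- *Regimen comparisons in general are biased.* Dose 1 contrasts keep everyone dosed with diary data. Groups 1 and 3 receive the same 7.5 µg at Dose 1, so selection into their Dose 2 tables is balanced in expectation.
- *The decline reported in Protocol 1.5 is a selection artefact.* That sentence is hedged and concerns solicited reporting overall, where the illustration shows little movement. The tables behind it are not in the documents.
- *The Phase 3 dose choice would change.* Protocol 7.8 records that a single 5 µg dose had already been chosen. Single-dose reactogenicity can be read from Dose 1 data, which carry no such selection.

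**Conclusion.** The point holds in a limited form. The Dose 2 Grade 3+ rate is conditional on not having had that outcome, confirmed, at Dose 1. Two readings are open to selection: a Dose 1 to Dose 2 decline in Grade 3+ events, and Dose 2 Grade 3+ contrasts between groups with different Dose 1 exposure (5.0 µg versus 7.5 µg, or active versus placebo). Per-participant reactogenicity over the whole priming course has no specified table.

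The actual size cannot be stated. Under the assumed 5% and 10% rates and correlations of 0.3 to 0.7, the Dose 2 table would show 64% to 90% and 59% to 87% of the true rate respectively. The figures depend on the latent-normal model, an unchanged true rate and full adherence to the bar, and the effect vanishes if reactions at the two doses are unrelated within a person. The consequence is for how the final report is read.

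**What to change.** Keep the per-dose tables and add two to SAP 9.1.1:

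1. Maximum solicited-AE grade after any priming dose, by study group and age group, over all dosed participants with at least one priming diary report, with Clopper-Pearson 95% CIs. This gives the overall summaries promised in SAP section 9 and Protocol 7.6.3.2 a concrete form for solicited AEs.
2. By study group, a cross-tabulation of Dose 1 maximum grade (rows) against Dose 2 maximum grade (columns), with a further column for Dose 2 not given. Selection into Dose 2 is then visible. It should be used in place of a comparison restricted to participants with both doses.

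Both use diary and dosing data already collected and change nothing in conduct. The cost is one or two extra tables, and a regimen-level rate that will look less favourable than either per-dose rate.
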